6.1.2 Dosage Adjustments and Stopping Rules

Dose adjustments will be based on the most recent local laboratory hemoglobin value (obtained on the day of the dosing visit or 1 day prior to the dosing visit), incidence of RBC transfusion in the last 21 days prior to the dosing visit, disease and chemotherapy status. An RBC transfusion includes either whole blood or packed RBC transfusion. Before the subject can be dosed, the site personnel will enter the relevant information into IVR/IWR System during a medication assignment call.

Automated programming in IVR/IWR System will determine if dose adjustment or withholding is required based on the dosing rules listed below. If dose adjustment occurs, all subsequent adjustments will be relative to the new dose. Rate of rise calculations will be based on the subject's hemoglobin value at the time of the last dose or for the last 3 weeks of study if more than 3 weeks have passed since the last dose.

If a subject stops myelosuppressive chemotherapy completely, IP will be discontinued within 3 weeks after the last dose of chemotherapy.

At any time during the study, the investigator may withhold or discontinue IP administration for any subject who experiences a severe or life-threatening adverse event reported by the investigator to be related to IP. The Common Toxicity Criteria for Adverse Events (CTCAE) grading scale will be used as a guide for grading the adverse events. Refer to Section 9 for more detail on adverse event reporting. If an investigator decides to discontinue IP (regardless of whether the subject will continue in the study), the site personnel are to enter this information into the IVR/IWR System.

IVR/IWR System will instruct investigators to withhold IP or to reduce the dose of IP according to the following criteria, which include non-responsiveness, rapid rate of rise of hemoglobin, and high hemoglobin value. These criteria are described as follows:

- A non-responder is defined as a subject who, after study day 35, receives 2 or more transfusions that are ≥ 21 days apart and ≤ 42 days apart. Non-responders will be discontinued from darbepoetin alfa if they are on the darbepoetin alfa treatment arm and will be switched to placebo (by IVR/IWR System).

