7.5 Treatment Period (Q3W Visits)

Study visits will occur every 3 weeks \pm 6 days with subcutaneous IP administration Q3W during the treatment period. IP will be discontinued within 3 weeks after the last dose of chemotherapy, or upon the determination of disease progression, whichever occurs first.

For all study visits during the treatment period, study procedures (eg, ECOG, laboratory sample draws) may be performed up to 1 day prior to IP dosing.

The following assessments and procedures will be performed during the treatment period:

- Vital signs and weight
- · The presence of a central or mid-line venous catheter
- ECOG performance status
- Assessment of disease progression
- Assess for signs and symptoms of clinically relevant TVE. If present, perform appropriate laboratory, diagnostic, and medical imaging for suspected TVE
- Imaging studies Q9W (or earlier if clinically indicated) until documented disease progression (see Section 7.1.6)
- Central laboratory tests: clinical chemistries and CBC with differential (including hemoglobin for statistical analyses), Tsat, ferritin, iron, and TIBC. Central laboratory tests will continue until the next Q3W study visit that occurs after the last dose of IP
- Local laboratory hemoglobin for IP dosing determination. Local laboratory hemoglobin testing will continue until the next Q3W study visit that occurs after the last dose of IP
- Access IVR/IWR system for medication assignment or to register a subject's discontinuation from IP (if applicable)
- Subcutaneous Q3W administration of IP
- Subjects who discontinued IP but have not had disease progression will continue Q3W visits and Q9W imaging studies until disease progression has been determined. Subjects who are unable to continue Q3W visits and Q9W imaging studies until disease progression should complete EOTP procedures at no later than their next Q3W visit and will be asked to enter the LTFU period

Concomitant medications, radiotherapy, anti-cancer therapy, anti-cancer surgery, and RBC transfusion information will be collected throughout the treatment period. AEs and SAEs will be collected up to 30 days after the last dose of IP.

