6.3 Per Protocol Sets

Since poor adherence to the protocol could have the potential to bias the results towards a conclusion of non-inferiority, a sensitivity analysis will be performed on a per protocol set to confirm results from the primary analysis set. The sensitivity analysis using this per protocol set will be performed for overall survival and **progression free survival**. The per protocol set will include subjects in the primary analysis set who meet all of the following additional criteria **(also see Appendix A):**

- had metastatic (Stage IV) or advanced stage IIIB with malignant pleural effusion (prior to Amendment 3) NSCLC
- no disease progression prior to study day 1
- no history of or current cancer diagnosis other than NSCLC
- had baseline pre-chemo scan prior to randomization (for PFS only)
- had an ECOG performance status of 0 or 1 at screening
- had a life expectancy > 6 months based on the judgment of the investigator at screening
- did not receive erythropoiesis stimulating agents within the 28 days prior to screening
- did not have a documented history of pure red cell aplasia
- dosed per protocol through week 7 with the correctly assigned investigational product (this includes receiving planned doses and dose adjustments per section 6.1.2 of the protocol)
- received first-line cyclic chemotherapy for NSCLC during the treatment period
- did not receive erythropoiesis stimulating agents, other than investigational product as defined in the protocol, during the treatment period.

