- To explore the impact of cross-in (placebo subjects who begin erythropoiesis stimulating agents at any point after randomization), an analysis will be performed that models erythropoiesis stimulating agent use as a time-dependent covariate in the stratified Cox regression. For subjects randomized to the darbepoetin alfa arm, the time-dependent covariate will be coded "1" throughout the time course (with the exception of subjects randomized to darbepoetin alfa who mistakenly receive placebo; they will be coded "0" throughout the time course unless they begin use of any erythropoiesis stimulating agent). For subjects randomized to the placebo arm, the time-dependent covariate will initially be coded "0" and change to "1" if and when they begin use of any erythropoiesis stimulating agent. Because the time-dependent covariate is based on information post-randomization, the results of this analysis will be interpreted with caution.
- To assess the impact of misspecifications of the stratification factors at randomization, a hazard ratio with 95% confidence interval will be estimated from an unstratified Cox regression with treatment group as a covariate along with covariates that represent the stratification factors. The values of the stratification factors will be determined from the case report forms rather than the IVRS. This analysis will only be done if there is evidence that there were errors in the IVRS stratification factors.
- To assess the impact of the early termination of the study, the primary analysis will be repeated for subjects who were still on-study or in long-term follow-up

as of June 7 and for subjects who were not impacted by the early study termination.

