Details of analyses provided to the Data Monitoring Committee, including the planned interim analyses, are not described or analyzed directly under this plan. These analyses were generated by PRA Health Sciences, Charlottesville, Virginia. An unplanned interim analysis conducted by an independent group at Amgen in Q4 2016 is also not covered in this plan.

14. Appendices

Appendix A. Technical Detail and Supplemental Information Regarding Statistical Procedures and Programs

Visit	Study day(s)	Window Definition	Interval (days)
Screening period	"-1"	Evaluation(s) within 21 days prior to the randomization date	21 to day -1
		Note: these should be on or after the date of consent, and should include history, vital sign, ECOG and other protocol specified measurements	
Randomization	-4 to 1	Randomization may occur on study day 1 or up to 4 day prior to study day 1.	1 day
		Note: Adverse events will be reported beginning from the data of randomization	
		Note: Subjects who progressed in the screening period (or prior to the screening period) are not eligible for randomization (protocol Section 7.1.6)	
Baseline/Study Day 1	1	Evaluation on Study Day 1 or last evaluation prior to Study Day 1 (if no value is available on Study Day 1). The first dose of study drug should be given on study day 1	1
		Note: Baseline hemoglobin value should be a central laboratory value. Note that a local laboratory hemoglobin value may be present in the database; this is used to confirm study eligibility and should not be used a the baseline hemoglobin value	
Treatment	Every 21	Dose 1: study day 1 (1-7)	Every 21
Period (Q3W visits)	days (+/- 6 davs)	Dose 2: study day 22 (15-27)	days(15-27 davs);
,	,	Dose 3: study day 43 (37-49)	duration is
		Dose 4: study day 64 (58-70)	n/u
		Dose 5: study day 85 (79-91)	
		Dose 6: study day 106 (100-112)	
		Dose 7: study day 127 (121-133)	
		Dose 8: study day 141 (135-147)	
		Dose 9: study day 162 (156-168)	
		Dose 10: study day 183 (177-189)	

	etc	
	Note: The treatment period, including study drug administration should last until disease progression	
	Note: Per protocol, study procedures (eg, ECOG, laboratory sample draws) may be performed up to 1 day prior to IP dosing	

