	Imaging studies will be performed every 9 weeks (± 7 days) or at any time symptoms suggestive of disease progression occur. Subjects who discontinue chemotherapy or IP should continue to be evaluated radiographically Q9W until disease progression.	Every 8-10 weeks until progression
EOTP	The EOTP visit is the next Q3W visit (± 6 days) after disease progression	n/d
Long-term follow-up (LTFU)	 LTFU begins after disease progression. Visits should occur at 3-month intervals (± 2 weeks). and	n/d
EOS	EOS is when a subject dies or is lost to follow- up or withdrawal or until 22 June 2017	n/d

n/d Not determinable – since many of these are event driven, the period for an individual subject cannot be determined apriori

Additional description of per protocol analysis

• Exclude subjects with EN 111 or EN 101 or OT 903

This excludes:

a) subjects that did not have NSCLC (OT 903)

b) subjects that did not have metastatic (Stage IV) or advanced stage IIIB with malignant pleural effusion NSCLC (prior to Amendment 3) (ie, subjects that had a lower grade tumor)

• Exclude subjects with EN 117A

This excludes subjects with disease progression prior to study day 1

• Exclude subjects with EN 202

This excludes subjects with a history of or current cancer diagnosis of a cancer type other than NSCLC

• Exclude subjects with EN 109 or EN 117 B

This excludes subject who did not have a baseline pre-chemo scan prior to randomization

- Exclude subjects with an ECOG performance status > 1 at screening (EN 113 or EN 103)
- Exclude subjects with EN 114 or EN 105

This should exclude subjects that had a life expectancy < 6 months based on the judgment of the investigator at screening

- Exclude subjects who received any erythropoiesis stimulating agents within the 28 days prior to screening (EN 223 or 218)
- Exclude subjects with EN 210 This should exclude subjects with a documented history of pure red cell aplasia
- Exclude subjects who are not dosed per protocol through week 7 (however, include subjects who received a planned dose adjustment per section 6.1.2 of the protocol)
- Exclude subjects who did not receive first line chemotherapy with an initial start date on or before Study day 1 and an end date after Study day 1

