- Exclude subjects who received ≥ 1 dose of an erythropoiesis stimulating agent(s) other than investigational product as defined in the protocol [eg, epoetin alfa (Procrit, Eprex or Epogen), epoetin beta (Micera), epoetin zeta (Retacrit)] during the treatment period (TA 507)
- Exclude subjects who received the incorrect investigational product (ie, randomized to placebo and received ≥ 1 dose of darbepoetin alfa; or, randomized to darbepoetin alfa and received ≥ 1 dose of placebo

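### Read literally, SAP Appendix A drops darbepoetin subjects from the per-protocol set for a placebo switch that Protocol 6.1.2 directs, while SAP 6.3 does not

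*SAP*

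**What the plan says.** Protocol 6.1.2 defines a non-responder as a subject with two or more transfusions, all after study day 35 and spaced 21 to 42 days apart. A non-responder on darbepoetin alfa comes off active drug and "will be switched to placebo (by IVR/IWR System"). A placebo-arm subject who meets the same definition simply stays on placebo.

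SAP 6.3 lists the per-protocol criteria. Its dosing criterion requires that the subject was "dosed per protocol through week 7 with the correctly assigned investigational product", and adds that "this includes receiving planned doses and dose adjustments per section 6.1.2 of the protocol". It refers the reader to Appendix A as well.

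SAP Appendix A, under the additional description of the per-protocol analysis, splits this into two bullets. The week-7 dosing bullet carries an exemption: "however, include subjects who received a planned dose adjustment per section 6.1.2 of the protocol". The last bullet is separate. It excludes subjects given the incorrect product and explains the term with an 'ie' clause covering placebo subjects with at least one darbepoetin dose "or, randomized to darbepoetin alfa and received ≥ 1 dose of placebo". That bullet has no time limit and does not mention 6.1.2.

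**The concern.** A darbepoetin subject switched by the IVR/IWR System has followed the protocol exactly, yet the last Appendix A bullet, as worded, excludes that subject. Under SAP 6.3 the switch is not a reason for exclusion, although the subject may still fail another criterion. The two SAP texts therefore describe different per-protocol sets.

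The exclusion is triggered by a post-randomisation outcome, repeat transfusion, and can act in one arm only. Other per-protocol criteria also use post-randomisation information, but they apply to both arms. SAP 6.3 gives the set a specific purpose: to confirm the primary result, because poor adherence could bias towards non-inferiority. If repeatedly transfused subjects have worse survival, removing them from the darbepoetin arm alone pushes the hazard ratio in the very direction the set is meant to guard against.

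**Working it through.** **Timing, from the documents alone**

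1. The first qualifying transfusion must come after day 35, so day 36 at the earliest (Protocol 6.1.2).
2. The second must be at least 21 days later: 36 + 21 = day 57.
3. Week 7 covers days 43 to 49, and the SAP Appendix A window for Dose 3 also ends on day 49.
4. The next scheduled dose is "Dose 4: study day 64 (58-70").

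Every directed switch therefore falls after the period that 6.3 examines.

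| Subject | SAP 6.3 | Last Appendix A bullet, literal |
|---|---|---|
| Darbepoetin, switched under 6.1.2, at least one placebo dose | Not excluded for the switch | Excluded |
| Placebo, same transfusion history | Not excluded | Not excluded |

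IP stops at the end of chemotherapy "or upon the determination of disease progression, whichever occurs first" (Protocol 7.5). Anyone who receives a switched dose is thus still progression-free, and the same subjects leave the OS and PFS sets.

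**Scale, from the plan's own figures**

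With 2700 deaths split 2:1, SE(log HR) = sqrt(1/1800 + 1/900) = 0.0408. This agrees with the stated power: ln(1.15)/0.0408 − 1.96 = 1.46, which gives 92.8% against the stated 93%.

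**Illustration of size; the inputs marked as assumed are not in the documents**

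- From the documents: 2:1 allocation, 51% one-year survival, drop-out 0.0511 (taken per year), 7-year accrual.
- Assumed: uniform accrual with cut-off at its end; true HR 1.00 and 1.15; non-responder share 5% or 10% in both arms; half or all of them given a placebo dose; non-responder hazard 1.0, 1.25, 1.5 or 2.0 times that of others; PFS median 4, 6 or 8 months; 20% of PFS events being deaths.
- Method: illness-death simulation, 1,000,000 subjects per cell. Darbepoetin-arm non-responders given placebo are removed if alive, progression-free and under follow-up past day 64.

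The share of the darbepoetin arm removed is 0.0107 to 0.0804. With a nominal arm of 2549 × 2/3 = 1699, that is 0.0107 × 1699 = 18 to 0.0804 × 1699 = 137 subjects, before other per-protocol exclusions.

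The ratio of per-protocol to as-randomised HR is 0.968–1.017 for OS and 0.980–1.029 for PFS. For OS, by assumed hazard:

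| Non-responder hazard relative to others | OS ratio |
|---|---|
| 1.0 | 1.003–1.017 |
| 1.25 | 0.996–0.999 |
| 1.5 | 0.983–0.997 |
| 2.0 | 0.968–0.996 |

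At hazard 1.0 the ratio exceeds 1 because those removed had to survive past day 64 to be removed. With 10% or 30% of PFS events as deaths (400,000 per cell, HR 1.00), the ranges are 0.967–1.018 for OS and 0.978–1.030 for PFS.

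A simpler exponential model gives a similar picture. With a 12.3-month median, true HR 1.0, 2–10% non-responders, hazards 1 to 2 times others and all non-responders alive at day 57 removed, the OS HR lies between 0.965 and 1.015, with simulation error about 0.006.

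The largest OS shift in the main grid is ln(0.968) = −0.0325. Against the planned SE this is 0.0325/0.0408 = 0.8.

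**The case against.** The strongest reply is that incorrect product means misallocated product. Appendix A elaborates 6.3, which speaks of correctly assigned product, and a dose the IVR/IWR System assigns is correctly assigned. The SAP supports this elsewhere. Its cross-in analysis (9.6.1) recodes darbepoetin subjects "with the exception of subjects randomized to darbepoetin alfa who mistakenly receive placebo", and the safety endpoint summary table (9.6) lists the non-response switch among dose changes, beside reductions and withholdings. That may well be the intent. But the explanatory clause in the last bullet has no such limit, and the authors wrote the 6.1.2 exemption into one bullet and not the other. Because 6.3 sends the programmer to Appendix A, the ambiguous bullet may well be the text that is coded. The clause also lacks its closing parenthesis, but nothing indicates that an exemption has been lost.

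Could the exclusion be deliberate, to avoid diluting exposure? That fits neither the word incorrect nor 6.3's treatment of 6.1.2 adjustments.

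The objections to the size are partly right. The 1.1% is not a floor: eligibility asks for only two further expected cycles, and IP ends within 3 weeks of the last chemotherapy dose, so many subjects may never reach a switched dose. The 0.8 figure belongs to the planned 2700 deaths, which 2549 subjects cannot supply. Under the simulation's accrual and cut-off, the hazard is −ln(0.51) = 0.673 per year and the total rate with drop-out is 0.724. The expected share dying is (0.673/0.724) × [1 − (1 − e^(−0.724×7))/(0.724×7)] = 0.75, or about 1,900 of 2549. Then SE = sqrt(1/1267 + 1/633) = 0.049 and the ratio is about 0.67. A smaller per-protocol set would have a larger SE still.

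**Conclusion.** The concern holds. The literal wording of the last Appendix A bullet conflicts with SAP 6.3 and excludes subjects who were treated as Protocol 6.1.2 directs. This rests on the text and the day count and needs no assumption. The size does: neither the switch rate nor the prognosis of non-responders is given, and the sign of any shift depends on that prognosis. Over the assumed grid the effect is a few percent of the hazard ratio in either direction and less than one standard error.

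The reach is limited to the per-protocol sensitivity analyses of OS and PFS. SAP 9.6.1 calls the OS sensitivity analyses exploratory, and 9.6.2 plans few on this set for PFS. It should still be fixed, because these analyses are meant to support a non-inferiority claim and the choice between two sets should not be left until results are known.

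**What to change.** In the last Appendix A bullet, define incorrect product as a product different from the one the IVR/IWR System assigned. Add one sentence saying that placebo doses assigned by the system under Protocol 6.1.2 do not exclude a subject. True dispensing errors stay excluded in both arms. SAP 6.3 needs no new rule, and the clinical switch rule is untouched.

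The cost is one clause and one sentence before database lock. Assignments and switches are already held in the IVR/IWR System, and SAP 9.6.10 already tabulates switches to placebo for non-response.

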Appendix B. Concomitant Medications

The following are the Concomitant Medications of Interest for this study:

- Antihypertensives
- Antimicrobials
- Antithrombotic agents
- Colony stimulating factors
- Epoetins
- Histone deacylating inhibitors
- Hypomethylating agents
- Iron
- Iron chelating agents
- Lenalidomide
- Methotrexates
- Platelets
- Thalidomide
- Thrombopoesis stimulating factors

Source: aranesp_oncology_moi.sas7bdat in: \\filesrv09\gsb\moi\statdata\products\2016Q4
